- H1 (negative parenting): Compared to control group parents, intervention group parents will report lower harsh parenting and lower control or overprotection at endline.
- H2 (positive parenting): Compared to control group parents, intervention group parents will report higher positive parenting at endline.
- H3 (Mediation — IPV & financial distress channel): A portion of the intervention's effect on parenting practices will be mediated by a reduction in IPV and financial stress.
- H4 (Mediation — mental health & relationship channel): A portion of the intervention's effect on parenting practices will be mediated by improvement in GHQ-6 scores and better relationship quality.

4. Measurement Schedule for this Sub-Study

The measurement schedule for variables relevant to this sub-study is summarised in Table 1. A critical feature of this design is that the proposed mediators, IPV and mental health, are observed at both baseline and endline, while parenting outcomes are observed at endline only, having been added to the endline survey before data collection commenced.

Table 1. Measurement Schedule

Variable	Baseline	Endline
Treatment assignment	✓	—
Intimate Partner Violence (IPV)	✓	✓
Mental health (GHQ-6)	✓	✓
Relationship strength & empathy	✓	✓
Financial distress	✓	✓
Sociodemographic covariates	✓	✓
Parenting practices	—	✓

5. Participants

Eligibility Criteria (Parent Trial)

Inclusion criteria: married and co-habiting husband-wife pairs; women aged 18-49 and men aged 18 or older; primary residence in a study cluster in Maharashtra, Andhra Pradesh, or Rajasthan; completion of at least primary schooling (4th grade); both partners provide written informed consent and agree to participate in six sessions, baseline and endline surveys, and SMS follow-ups; both partners understand the local language used in sessions; no plans for relocation or prolonged absence before endline.

Exclusion criteria: either partner under 18 years; refusal of consent or unwillingness to participate by either partner; serious physical or mental condition preventing safe active participation.

Parenting Sub-Study Subsample

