For the parenting analysis, we will restrict the analytic sample to couples with at least one child residing in the household at the time of the endline survey. Where a household includes multiple children, the respondent will be asked to answer parenting questions regarding the youngest school-age child (defined as the youngest child aged 5-18 currently enrolled in school).

Unit of Analysis

Parenting questions will be administered separately to both the mother and the father. All primary analyses will be conducted separately for mothers and for fathers, generating gender-specific ITT estimates.

6. Measures

Outcome Measures: Short-Egna Minnen Beträffande Uppfostran Questionnaire – Parent Version (s-EMBU-P)

Parenting practices will be assessed using a 10-item subset of the 23-item long s-EMBU P (Arrindell et al., 1998). The s-EMBU-P is a popular scale for measuring parenting styles and has been validated across community and clinical samples in the Indian subcontinent (Yangzong et al., 2017; Saleem et al., 2015). Items will be translated into the relevant local languages (Marathi, Telugu, Hindi/Rajasthani) using standard forward-back translation procedures.

Table 2. s-EMBU-P Subscales and Items

The following are statements about things that may happen in a family. Please select how often each typically occurs in your home. Think about [your youngest child] when answering.

Response scale: 1 = No, Never, 2 = Yes, but seldom, 3 = Yes, often, 4 = Yes, most of the time

No.	Item	Subscale	Coding
1	I get angry with my child without letting him/her know the reason.	Rejection/ Harsh parenting (HP)	Higher = worse
2	I use physical punishment to discipline my child.	Rejection/ Harsh parenting	Higher = worse
3	I criticize my child and tell him/her how lazy and useless he/she is in front of others.	Rejection/ Harsh parenting	Higher = worse
4	I punish my child hard, even for small offences.	Rejection/ Harsh parenting	Higher = worse
5	I try to comfort and encourage my child if things go badly for him/her.	Emotional warmth/ Positive parenting (PP)	Higher = better
6	I use words and gestures to show that I like my child.	Emotional warmth/ Positive parenting	Higher = better
7	I praise my child.	Emotional warmth/ Positive parenting	Higher = better
8	I am proud when my child succeeds in something he/she has undertaken.	Emotional warmth/ Positive parenting	Higher = better

No.	Item	Subscale	Coding

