9	I put strict limits on what my child is and is not allowed to do, to which I then adhere rigorously.	Overprotection/control (C)	Higher = worse
10	When my child comes home, he/she has to account for what he/she had been doing to me.	Overprotection/control	Higher = worse

Each subscale score will be computed as the mean of its constituent items. For composite analyses, the negative parenting subscales (C, HP) will be reverse-coded prior to averaging, so that higher values across all composite indices indicate better parenting outcomes.

Mediator Variables

Intimate Partner Violence (IPV): IPV is measured using the instrument employed in the main ECOVI trial, which includes physical, sexual, economic, and emotional/psychological IPV subscales consistent with WHO measurement standards. Women's experience of IPV will be assessed.

For the mediation analysis, we will use the relevant IPV composite score (or sub-scores for specific IPV types in sensitivity analyses). The mediating variable will be the change score $\Delta\text{IPV} = \text{endline IPV} - \text{baseline IPV}$, with negative values indicating a reduction in IPV.

Mental Health (GHQ-6): Psychological distress is measured using the General Health Questionnaire-6 (GHQ-6) adapted for field use. The GHQ-6 is scored 1-5, with higher scores indicating greater distress.

The mediating variable will be the change score $\Delta\text{GHQ-6} = \text{endline GHQ-6} - \text{baseline GHQ-6}$, with negative values indicating a reduction in distress or improvement in mental health.

Relationship quality: Change in the composite Relationship Satisfaction Index (adapted for the study), measuring perceptions of the couple as a team, happy in the relationship, and the strength of the relationship. The scale is scored 1-5, with higher scores indicating a stronger perceived relationship.

For mediation analyses, we will construct change scores for each construct as $\Delta\text{RQ} = \text{endline RQ} - \text{baseline RQ}$, where positive values indicate improvements in relationship functioning.

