Financial distress: Financial distress is measured as the frequency and severity of household economic hardship over the past six months (scale 1–6, with higher values indicating lower distress). The measure captures multiple dimensions, including perceived financial stress, food insecurity, difficulty meeting basic needs, reliance on borrowing or asset depletion, and indirect impacts on healthcare access and children's well-being (e.g., school absenteeism, child labour, and missed meals).

The mediating variable will be defined as the change in financial distress calculated as $\Delta\text{FD} = \text{endline FD} - \text{baseline FD}$, where positive values indicate improvements in financial situation (i.e., reduced distress).

Covariates

The following baseline variables will be included as covariates in all primary regression models:

- Respondent age
- Respondent education
- Respondent SES
- Residential type (rural vs. urban)
- Living arrangement (co-residing with in-laws vs. not)
- Gender norms
- State fixed effects (Maharashtra, Andhra Pradesh, Rajasthan)

In addition, baseline values of each mediator will be included in both mediator and outcome models to account for regression to the mean and strengthen identification.

7. Analytical Strategy

Primary ITT Analysis

The primary analysis estimates the Intent-to-Treat (ITT) effect of the intervention on each APQ subscale score and the combined APQ score. We will estimate the following OLS regression model for each subscale:

$$Y_i = \alpha + \beta \cdot T_i + \gamma \cdot X_i + \epsilon_i$$

where Y_i is the standardised APQ score of individual i at endline; T_i is a binary indicator of treatment assignment (1 = intervention, 0 = control); X_i is a vector of pre-specified baseline covariates, and ϵ_i is the error term. Standard errors will be clustered at the community level to account for the cluster randomisation design. The coefficient β is the ITT estimate of interest.

Multiple outcomes correction: To address the multiple testing problem arising from five APQ subscales, we will pre-specify a composite parenting index as the primary outcome for each sign direction. The *Negative Parenting Index* will be the simple mean of standardised CP, ID, and PMS scores (reverse-coded so that higher = worse parenting). The *Positive Parenting Index* will be the simple mean of standardised PP and PI scores. The five individual subscale regressions will be reported as secondary outcomes.

Mediation Analysis

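### The protocol fixes two incompatible directions for the Negative Parenting Index, a primary outcome, so the sign of its treatment effect can be read backwards

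*Protocol*

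**What the plan says.** Section 6 (Measures), Table 2, gives ten items scored 1 to 4: "Response scale: 1 = No, Never, 2 = Yes, but seldom, 3 = Yes, often, 4 = Yes, most of the time". Every harsh-parenting item (1 to 4) and both control items (9 and 10) carry the coding note that higher is worse. Examples are "I use physical punishment to discipline my child. Rejection/ Harsh parenting Higher = worse" and "Overprotection/control (C) Higher = worse".

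The scoring paragraph below Table 2 then says that, for composite analyses, "the negative parenting subscales (C, HP) will be reverse-coded prior to averaging", and gives the purpose: "so that higher values across all composite indices indicate better parenting outcomes".

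Section 7 (Analytical Strategy, multiple outcomes correction) makes one composite per sign direction the primary outcome. It defines the Negative Parenting Index as the mean of standardised CP, ID and PMS scores, "reverse-coded so that higher = worse parenting".

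Section 3, hypothesis H1, predicts that "intervention group parents will report lower harsh parenting and lower control or overprotection at endline". This is worded in the native direction of the items and does not say how the index is coded.

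**The concern.** Two statements fix the direction of the same primary outcome and they disagree. Under section 6 a high Negative Parenting Index means good parenting. Under section 7 it means bad parenting. Section 7 also attaches a reversal to a label that, for the items in Table 2, describes the unreversed score.

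The quantity at stake is the sign of beta, the intention-to-treat coefficient, which is estimated separately for mothers and for fathers. The same sign carries into the average causal mediation effect (ACME) and the average direct effect (ADE) for every mediator analysed against this index. The mediators themselves run in different directions: improvement is a negative change for IPV and GHQ-6, and a positive change for relationship quality and for the financial measure. A wrong outcome sign would therefore be harder to spot in the mediation tables than in a single regression.

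**Working it through.** The protocol states no effect size, power or sample-size figure for this sub-study, so there is no figure to reproduce. The check is on direction.

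**Step 1. What reversal does to an item.** On a 1 to 4 scale the reversed score is x′ = 5 − x, so 1, 2, 3, 4 become 4, 3, 2, 1. A parent who uses physical punishment most of the time scores 4 natively and 1 after reversal. Higher is then better.

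**Step 2. What it does to the index.** A subscale mean m becomes 5 − m. Its standardised value is z′ = [(5 − m) − (5 − m̄)] / s = −z. With the index built from HP and C, (z′_HP + z′_C)/2 = −(z_HP + z_C)/2. The reversed index is exactly the negative of the native one.

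**Step 3. What it does to the estimates.** In Y = α + βT + γX + ε, replacing Y by −Y gives β′ = −β and flips the sign of every residual. The cluster-robust variance uses products of residuals, so the standard error and two-sided p-value are the same. In a linear mediation model with treatment-to-mediator path a and mediator-to-outcome path b, reversal leaves a alone and gives b′ = −b. Hence ACME′ = −ACME and ADE′ = −ADE.

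**Step 4. Numerical confirmation on assumed data.** All inputs here are assumptions chosen only to show the sign: 150 clusters of 15 respondents, 75 clusters per arm, a true reduction in harsh parenting and control, four HP items and two C items, and OLS with cluster-robust standard errors and no covariates.

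| Coding | beta | SE | two-sided p |
|---|---|---|---|
| Native, higher is worse | −0.233 | 0.042 | 3.2 × 10⁻⁸ |
| Reversed (5 − x), higher is better | +0.233 | 0.042 | 3.2 × 10⁻⁸ |

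Only the sign differs. The 0.233 says nothing about this trial.

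**Step 5. The possible readings, for a true benefit.**

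| Scores used | Label used to read them | Sign of beta | Conclusion |
|---|---|---|---|
| Unreversed | higher is worse (section 7 label) | negative | benefit, correct |
| Reversed | higher is better (section 6) | positive | benefit, correct |
| Reversed | higher is worse (section 7 operation and label together) | positive | harm, wrong |
| Unreversed | higher is better (section 7 end state read by section 6) | negative | harm, wrong |

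The third row is section 7 followed to the letter on the Table 2 items. The fourth arises if the analyst follows the section 7 label and the reader relies on section 6.

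**The case against.** The strongest reply is that the section 7 sentence does not mention HP or C. It names CP, ID and PMS and refers to APQ subscales, whereas section 6 specifies the s-EMBU-P with HP, PP and C. The protocol does not give the native direction of CP, ID or PMS. A reader might infer that the section 7 sentence contradicts itself exactly as written. The document does not support that: if those scores ran with higher as better, reversing them to make higher worse would be coherent. The internal contradiction appears only once HP and C are put in. That step is unavoidable, however, because CP, ID and PMS cannot be formed from the ten items to be collected. The conflict with section 6 over the end state needs no substitution, since section 6 covers all composite indices.

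Second, a careful analyst has clues. The index name, H1 and the stated purpose in section 7 all point to higher is worse. The individual subscale regressions are secondary outcomes, and section 6 reverses only for composites, so an index whose sign disagreed with its own components would be visible. This stands as a reason to call the misreading a risk and not a certainty. It does not settle the matter, because opposite signs for index and components are exactly what the section 6 rule would correctly produce.

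Third, coding direction might be left to a statistical analysis plan. That would answer a complaint that the direction was missing. Here it is stated twice, incompatibly.

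**Conclusion.** The point holds as a conflict between two stated rules for a primary outcome. Sections 6 and 7 give the Negative Parenting Index opposite directions. When the index is built from HP and C, the section 7 operation and label also exclude each other. The consequence is a possible reversal of the sign of beta, the ACME and the ADE on this index, for mothers and for fathers.

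The limits are these. Magnitude, standard error and two-sided p-value are unaffected, so a reader who inferred that the test is biased or its error rate inflated would go too far. A size in standard deviations cannot be given: the protocol has no effect size for this sub-study, and any figure would simply be twice whatever effect was assumed. The direction of the Positive Parenting Index is not in dispute. Nor does the protocol show that one of the two directions is the only correct one. The conclusion rests on one assumption, that the index will be built from the HP and C items in Table 2. It is needed only for the contradiction inside section 7, not for the conflict between the sections.

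**What to change.** Make these edits together, before endline data are collected.

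- In section 7, define the Negative Parenting Index as the mean of the standardised s-EMBU-P subscales HP and C, replacing CP, ID and PMS. Correcting the direction alone would leave a primary outcome that cannot be computed from Table 2.
- Set one direction in sections 6 and 7. One option is to leave this index unreversed, so that higher is worse and benefit is beta < 0, in line with its name and H1. This means deleting the reverse-coding from the section 7 definition and limiting the section 6 reversal to the combined score. The other option, equally valid, is to reverse HP and C in every composite, so that higher is better and benefit is beta > 0, and to change the section 7 label to match.
- State the beneficial sign of beta for each index. Under the first option this is negative for the Negative Parenting Index and positive for the Positive Parenting Index and the combined score. Add that the ACME and ADE on each index are read in the same direction.

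The cost is a few sentences of protocol wording. Data collection, sample and model are unchanged.

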With respect to discipline specifically, evidence indicates that the effects of IPV on harsh parenting are partly mediated by maternal depression. One longitudinal study of 705 participants found that the path from IPV exposure to harsh parenting ran through depressive symptoms (Gustafsson et al., 2012; Sousa et al., 2022), establishing maternal mental health as a key mechanism linking violence in the couple relationship to parent-child interactions. A notable gap in this literature is the lack of evidence on fathers. Relatively little is known about whether paternal exposure to or perpetration of IPV similarly affects men's own parenting practices through mental health or other channels.

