2.5 The ECOVI Intervention and its Potential Effects on Parenting

The "Let Us Grow Together: Economic Wellbeing for Families" intervention integrates financial literacy education (budgeting, savings, joint financial planning) with gender-transformative content (equitable household roles, communication skills, conflict resolution, and fostering empathy between spouses) across six structured community-based sessions for couples. The intervention is delivered by trained male-female facilitator pairs in group settings of approximately 15 couples. Between sessions, SMS reinforcements are sent to participants to sustain engagement. Sensitive content on IPV and its triggers is delivered in gender-segregated settings to encourage reflection and reduce defensiveness.

Based on the conceptual framework established in the literature above, we propose three pathways through which this intervention may affect parenting practices:

Improved relationship channel: Improved communication, gender norms, and relationship quality may translate directly into better parenting behaviours, independent of changes in IPV or mental health. Similar to Bandedereho (Doyle et al., 2023), where couples appeared to apply learned communication skills in interactions with their children, ECOVI participants who learn to communicate more equitably and empathetically may also adopt more positive parenting practices as a by-product.

IPV reduction channel: The intervention is designed to reduce IPV and improve couple dynamics. As documented in the literature, reductions in household violence and conflict reduce parenting stress and emotional exhaustion, thereby enabling more consistent, warm, and non-violent discipline.

Mental health channel: The intervention targets psychological distress (measured via GHQ-6) as a primary outcome in the ECOVI mental health sub-study (NCT07108049). Improvements in mental health, themselves partly driven by reductions in IPV and improvements in relationship quality, can increase parenting capacity, as demonstrated by Baranov et al. (2020) and Goodman et al. (2023).

Financial distress reduction channel: The intervention has a direct goal of reducing financial distress by improving economic decision-making and through practical household financial management exercises as part of the financial literacy pillar. As documented in the literature, reductions in financial stress may lead to more positive and non-violent discipline.

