To investigate potential mechanisms, we will implement causal mediation analysis following Imai, Keele, and Tingley (2010) and Steinert et al. (2020). This framework decomposes the total treatment effect into:

- the Average Causal Mediation Effect (ACME) (indirect effect through the mediator), and
- the Average Direct Effect (ADE) (effect not operating through the mediator).

The ACME will capture the extent to which the intervention affects parenting outcomes through changes in the mediator (e.g., reductions in IPV or improvements in mental health), rather than the mediator level itself.

Mediator specification: All mediators will be defined as change scores (ΔM) between baseline and endline. This approach captures treatment-induced changes in the mediator and strengthens temporal ordering

between treatment, mediator, and outcome. Each mediator will be analysed separately in the primary mediation models.

Random assignment of the intervention ensures unbiased estimation of the total effect. However, because mediators are not randomised, identification of mediation effects relies on the sequential ignorability assumption, which cannot be directly tested and may be violated if unobserved factors jointly influence the mediator and outcome. We therefore interpret mediation estimates cautiously as indicative of plausible pathways rather than definitive causal mechanisms.

To assess the robustness of mediation estimates to violations of sequential ignorability, we will conduct formal sensitivity analyses following Imai et al. (2010b), as implemented in Steinert et al. (2020).

Specifically:

- We will estimate the sensitivity parameter (ρ), representing the correlation between the error terms of the mediator and outcome models.
- We will report the value of ρ at which the ACME would be reduced to zero.
- We will also report the corresponding R^2 -based measure, indicating the proportion of variance in both mediator and outcome that an unobserved confounder would need to explain to invalidate the mediation effect.

Following prior work, mediation results will be interpreted as more robust when the ACME remains non-zero under relatively large values of ρ or substantial variance explained by a hypothetical confounder.

As an additional exploratory analysis, we will implement structural equation modelling (SEM) to examine multiple mediating pathways simultaneously, following the approach of Steinert et al. (2020). SEM enables:

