- the simultaneous estimation of relationships between treatment, multiple mediators, and outcomes, modelling of mediators as interrelated processes, including indirect and sequential pathways, and incorporation of latent constructs where appropriate.
- This approach complements the single-mediator causal mediation models by allowing us to evaluate whether mediators operate jointly and through indirect chains (e.g., relationship quality → mental health → parenting), as demonstrated in prior work. However, consistent with the limitations of the data (particularly the lack of temporal separation between mediators and outcomes), SEM results will be interpreted as descriptive of pathway structure rather than causal identification.

8. Ethical Considerations

This sub-study is conducted under the ethical approval obtained for the main ECOVI trial by the Technical University of Munich and PCI India. The addition of parenting questions to the endline survey constitutes a minor amendment to the data collection instrument; we confirm that relevant ethics board approval will be obtained prior to fielding the amended endline survey. All participants will provide written informed consent, will be informed of their right to withdraw at any time, and will be assured of the confidentiality of their responses.

9. References

- Alloy, L. B., Abramson, L. Y., Tashman, N. A., Berrebbi, D. S., Hogan, M. E., Whitehouse, W. G., Crossfield, A. G., & Morocco, A. (2001). Developmental Origins of Cognitive Vulnerability to Depression: Parenting, Cognitive, and Inferential Feedback Styles of the Parents of Individuals at High and Low Cognitive Risk for Depression. *Cognitive Therapy and Research*, 25(4), 397–423. <https://doi.org/10.1023/A:1005534503148>
- Anderson, K. M., & Danis, F. S. (2006). Adult Daughters of Battered Women: Resistance and Resilience in the Face of Danger. *Affilia*, 21(4), 419–432. <https://doi.org/10.1177/0886109906292130>
- Arrindell, W. A., Sanavio, E., Aguilar, G., Sica, C., Hatzichristou, C., Eisemann, M., ... & van der Ende, J. (1999). The development of a short form of the EMBU: Its appraisal with students in Greece, Guatemala, Hungary and Italy. *Personality and individual Differences*, 27(4), 613–628.

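### The primary single-mediator model for mental health is confounded by IPV and relationship change, which the protocol itself says drive mental health

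*Protocol*

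**What the plan says.** Section 7 (Mediation Analysis) defines every mediator as a change from baseline to endline and states: "Each mediator will be analysed separately in the primary mediation models". Section 6 (Covariates) adds baseline mediator values to the mediator and outcome models. It does not add the concurrent changes in the other mediators.

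The protocol also describes how the mediators relate to one another:

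- Section 2.5, mental health channel: "Improvements in mental health, themselves partly driven by reductions in IPV and improvements in relationship quality, can increase parenting capacity".
- Section 2.5, relationship channel: better communication and relationship quality "may translate directly into better parenting behaviours, independent of changes in IPV or mental health".
- Section 2.2, citing a longitudinal study: "the path from IPV exposure to harsh parenting ran through depressive symptoms".
- Section 7, on the structural equation model (SEM): "indirect chains (e.g., relationship quality → mental health → parenting" is given as an example of what the model may show.

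On identification, Section 7 says that sequential ignorability "may be violated if unobserved factors jointly influence the mediator and outcome". It plans a sensitivity analysis on ρ and R² and promises cautious interpretation. The only joint model is the SEM, which allows "modelling of mediators as interrelated processes, including indirect and sequential pathways". It is labelled exploratory and is to be read as descriptive.

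**The concern.** If relationship quality and IPV change in response to treatment, move GHQ-6, and also move parenting by other routes, they confound the GHQ-6 to parenting association. Adjusting for their baseline values does not remove this, because the confounding comes through their change after randomisation. The stated caveat names unobserved factors only, whereas these confounders are measured and are the trial's own mediators.

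At stake is the answer to RQ-4 and the mental-health half of H4. A GHQ-6 that merely tracks a better relationship or less violence would be reported as a channel in its own right.

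There is a second mismatch, of estimand. The single-mediator relationship ACME collects every path that starts with relationship quality, including those through GHQ-6 (and through IPV, if relationship quality drives it). Section 2.5 defines the relationship channel as the part that bypasses both.

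**Working it through.** The protocol states no path coefficient, effect size or power for the mediation analysis, so there is no figure to reproduce. The structure below is the protocol's; every number is an assumption.

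**Structure.** Treatment T affects relationship R, IPV reduction I, finances F and mental health G. All four affect parenting Y. R and I also affect G. No other links.

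**Assumed sizes.** All variables are coded so that higher is better. T→R, T→I and T→F are 0.2 each; direct T→G is 0.1; each mediator→Y is 0.2. There is no residual direct effect, and errors are independent with SD 1. The links R→G and I→G both equal λ.

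**Formulas.**

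- Effect of T on G: t = 0.1 + 2 × λ × 0.2.
- Effect truly transmitted by GHQ-6: t × b, where b is the effect of G on Y.
- Coefficient of G when Y is regressed on T and G only: b + (λ × 0.2 + λ × 0.2) / (1 + 2λ²). The second term is the confounding.
- Single-mediator ACME: t × that coefficient.
- Total effect: 3 × 0.2 × 0.2 + t × b.

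| Case | t | Total | True via GHQ-6 | Coefficient of G | ACME | Ratio |
|---|---|---|---|---|---|---|
| λ = 0.1, b = 0.2 | 0.14 | 0.148 | 0.028 (19%) | 0.2 + 0.04/1.02 = 0.239 | 0.0335 (23%) | 1.2 |
| λ = 0.3, b = 0.2 | 0.22 | 0.164 | 0.044 (27%) | 0.2 + 0.12/1.18 = 0.302 | 0.0664 (40%) | 1.5 |
| λ = 0.3, b = 0 | 0.22 | 0.120 | 0 (0%) | 0.12/1.18 = 0.102 | 0.0224 (19%) | – |

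A simulation of the same model with 4,000,000 observations gave ACMEs of 0.0335, 0.0661 and 0.0225. With no links among the mediators there was no bias.

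**Other mediators, λ = 0.3.** The relationship ACME is 0.2 × (0.2 + 0.3 × 0.2) = 0.052, which is its correct total indirect effect. The part that bypasses GHQ-6 and IPV is 0.2 × 0.2 = 0.040. The IPV ACME is likewise 0.052 and unbiased. Financial distress is unbiased at 0.040. IPV becomes biased only if relationship quality also drives IPV. In a simulated case with R→I 0.3, R→G and I→G 0.5 and F→G 0.3, its share was 48% against a true 37%.

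**Effect of adjustment.** Adding R and I to the GHQ-6 outcome model returns the coefficient of G to b. The estimate is then 0.22 × 0.2 = 0.044, or 0 when GHQ-6 is inert; both are correct.

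**What ρ shows.** Omitting R and I at λ = 0.3 induces an error correlation of 0.12 / √(1.18 × 1.12) = 0.10. Here 1.12 = 1 + 3 × 0.2² is the outcome error variance. In the inert case, the ρ that sets the ACME to zero is also 0.10. The planned report would print that value with no yardstick showing that the measured mediators alone account for it.

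**The case against.** The strongest reply is that the plan is already modest. It calls the mediation results indicative, plans a ρ analysis, and adds an SEM that names the very chain at issue. In a linear model ρ does absorb omitted mediators, because they enter the two error terms, so it would be wrong to say that ρ cannot speak to this problem. That stands. What is missing is a comparison of ρ with the correlation that the measured mediators produce, and a caveat that names them.

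Three stronger readings are tempting, and the documents do not support them.

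- A reader might infer that all four ACMEs are biased. Section 2.5 states links in one direction, from IPV and relationship quality to mental health. With those alone, the other three ACMEs are valid total indirect effects. Section 2.4 lists marital conflict and poor communication as risk factors for violence, which hints at a relationship-to-IPV link, but only as background.
- A reader might infer that the plan double-counts. RQ-2 to RQ-5 ask about each channel separately, and nothing says the ACMEs will be added or ranked. Nor is their sum a test of bias. In a simulated pure chain it was 201% with no ACME biased. With λ = 0.3 and a residual direct effect of 0.05 it was 98%, although GHQ-6 was still overstated (31% against 21%).
- A reader might infer that the mediation intervals will ignore clustering. The protocol does not say so, and that detail may sit in the SAP.

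It is also fair that Section 2.5 routes IPV to parenting through stress and exhaustion, which GHQ-6 may partly capture. If IPV had no route outside GHQ-6, the excess would halve: (0.2 + 0.02/1.02)/0.2 = 1.10 at λ = 0.1 and (0.2 + 0.06/1.18)/0.2 = 1.25 at λ = 0.3. It would not vanish, because the relationship route is stated to be independent of mental health. Section 2.2 also calls the IPV path only partly mediated by depression.

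**Conclusion.** The point holds for mental health. Under the protocol's own causal account, the primary GHQ-6 ACME is confounded by measured, treatment-affected mediators and can be non-zero when GHQ-6 does nothing. For IPV the same holds only if relationship quality drives IPV. The relationship ACME is a legitimate quantity, but not the channel that Section 2.5 defines.

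The illustrated excess of 1.2 to 1.5 times, and the 19% share for an inert GHQ-6, rest wholly on assumed coefficients, linearity, no unmeasured confounding and links in the stated direction. The documents fix the existence and direction of the links, not their size. Because the protocol precedes endline data collection, the change can still be fully pre-specified.

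**What to change.** In Section 7, make the main mediation analysis an outcome model that contains all four mediators and their baselines. From it, report the joint indirect effect through the set and an interventional indirect effect for each mediator. At minimum, adjust the GHQ-6 outcome model for concurrent IPV and relationship change.

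Keep the single-mediator ACMEs, labelled as descriptive total indirect effects that do not add up. Benchmark ρ against the error correlation attributable to the measured mediators. Extend the sequential-ignorability caveat to name IPV and relationship change as confounders of the GHQ-6 path. State whether RQ-2 concerns the total indirect effect of relationship quality or the part that bypasses IPV and mental health.

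The cost is wording and analysis code, with no new data. Intervals will be somewhat wider, and the estimand for each channel changes slightly. The joint effect alone does not answer the channel-specific questions, so the per-mediator effects are needed beside it. The analysis still relies on no unmeasured confounding and on an assumed ordering of mediators measured at the same visit, a limit it shares with the planned SEM.
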